8.2. Secondary Objectives

 To retrospectively assess the efficacy consequences of NA and OIA, after adjusting for baseline characteristics and other confounders, overall and by cohort, on the odds of becoming unsuppressed, in subjects with and without resistance development. The protocol definition of unsuppressed is: HIV RNA>50 copies/mL in two consecutive measures within regimen duration, occurring within the observation period; among patient-regimens with HIV RNA ≤50 copies/mL at the start of the regimen if the regimen started during the observation period, or at the start of the observation period if the regimen started before the observation period.

In order to evaluate the odds of becoming unsuppressed (with or without resistance development), laboratory / monitoring data shall be collected.

• To retrospectively assess the effect of NA and OIA on the odds of hospitalization, after adjusting for baseline characteristics and other confounders, overall and by cohort.

In order to answer this objective, hospitalization data of all patient-regimens included in the study shall be collected.

To retrospectively assess the impact of NA and OIA on mean monthly ART plus hospitalization costs (Gross Domestic Product [GDP] Purchasing Power [PP] converted current prices), after adjusting for baseline characteristics and other confounders, overall and by cohort.

Ideally, hospitalization and ART costs will be collected at the center level. If not possible, hospitalization costs will be collected from publicly available national lists of diagnosis-related groups (DRGs) and ART costs from IMS databases of each participating country.

To assess the impact of STR versus non-STR on:

- 1. becoming unsuppressed (defined as above)
- 2. being hospitalized
- 3. costs (ART plus hospitalization costs)

To retrospectively quantify ART prescription errors during the first 48 hours of hospitalization of HIV-1 adult patients, overall and according to the cohort. Prescription errors will be evaluated by reviewing all prescriptions made during the first 48 hours of every hospitalization episode included. Investigators shall review all medication orders during this period to identify ART prescription errors. Errors will be classified as

- 1. Absence / incomplete regimen when the regimen prescribed is incomplete (e.g. when the physician prescribes only one PI/r) or when the regimen is not prescribed although it should have been.

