- incorrect dosage (including renal dose adjustment) when the dosage of a component/co-formulation of the regimen is not correct, i.e. the dosage prescribed does not exist
- 3. incorrect schedule when the schedule mentioned by the physician is not adequate to the regimen prescribed
- 4. incorrect formulation when the pharmaceutical form prescribed is not available
- 5. duplication of ART therapy
- 6. non-recommended drug-drug combinations (ART-ART and ART-non-ART), as suggested by Yehia et al. {27744, 22}. Non-recommended drug-drug combinations (between antiretroviral agents and/or antiretroviral agents and other drugs simultaneously) are available on the HIV Drug interaction website and are shown in red as contra-indicated:www.hiv-druginteractions.org/Interactions.aspx

9. **RESEARCH METHODS**

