9.2. Population

The population being studied are HIV-1 infected adult patients on ART, recruited from centers in Italy, Portugal, Spain and UK by Investigators that have expertise in the management of HIV infection.

Adherence study

HIV-1 infected adults who received ART between 1st January 2009 and 31st December 2013 for at least 90 days.

Inclusion criteria:

- HIV-1 infected
- Aged 18 or above at the beginning of the observation period
- Able and willing to provide informed consent
- At least one pharmacy refill in 2013
- Being followed at the center at the time of recruitment
- Has been on an ART regimen recommended by EACS v 7.0 {27774}, which contains two NRTI plus one NNRTI or two NRTI plus one PI/r, or Stribild, and which was taken once daily for at least 90 days on 31st December 2013.
- Availability of a complete electronic history of pharmacy refills throughout the observation period.

Exclusion criteria:

- Subject participation in an interventional study during the observation period
- Subject on a non-pill formulation during the observation period
- Subject on off-ART periods (ART holidays) during the observation period.

Prescription errors sub-study:

Subjects enrolled in the sub-study do not need to be participating in the adherence study in order to be eligible.

Inclusion criteria:

- HIV-1 infected patients who were hospitalized, at least for a minimum of 48 hours between 1st January 2012 and 29th December 2013 and who received, or should have received, an ART regimen during the first 48 hours of the hospitalization episode;
- Aged 18 or above at the beginning of the hospitalization episode;
- Able and willing to provide informed consent
- Availability of complete history of medication (ART and non-ART) prescribed during the first 48 hours of the hospitalization episode.

Exclusion criteria:

• Subject participation in an interventional study during the observation period

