- 2. Matching algorithm choice: The nearest neighbor algorithm or the nearest neighbor within a specified caliper distance algorithm will be used as a matching algorithm. The nearest neighbor matching selects for matching to a given STR subject the non-STR subject whose propensity score is closest to that of the STR subject. Nearest neighbor matching within a specified caliper distance is similar to nearest neighbor matching with the further restriction that the absolute difference in the propensity scores of matched subjects must be below some pre-specified threshold (the caliper distance) {27758} {27759}. The choice between one of these approaches will rely on how much data will be collected.
- 3. Sample balance diagnosis: Sample balance will be checked using the methods proposed by Ho et al. including standardized means, comparing higher-order moments, propensity-score summary statistics or empirical quantile-quantile plots for each variable {27772}.
- 4. Matching: Assign the matching membership and retain the propensity score for the case where further adjustment is needed.

Prescription errors sub-study

In this sub-study, unit of analysis will be a hospitalization episode of HIV-1 infected adult (due to any reason) in which there was a prescription of ART during the first 48 hours. Two cohorts will be considered: (i) STR and (ii) non-STR. Subjects will be enrolled that were hospitalised between 1st January 2012 and 29th December 2013.

For the prescription errors sub-study, subject selection will involve the following steps, to be initiated as soon as hospital approval has been granted at each site:

- 1. Search in the hospital registry to identify all hospitalization episodes of HIV-1 infected patients with admission date 1st January 2012 and 29th December 2013.
- 2. Check Inclusion criteria once identified, the Investigator will check whether those hospitalization episodes meet the inclusion criteria.

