Inpatient care (all episodes performed in the observation period)	 For each episode: Date of admission Admission diagnosis Date of discharge Destination at discharge Event code (DRG) ICD-9 or ICD-10 code (primary and secondary) Total cost of hospitalisation, including medications
Antiretroviral treatment pharmacy refills (for each valid patient-regimen)	 For each drug of each regimen: Date of refill (dd/mm/yyyy) scientific / generic name (which includes active principles, dosages, pharmaceutical forms), Quantity dispensed
Adverse Drug Reactions	 For each episode Adverse Drug Reaction description Seriousness Start and End dates or ongoing Relation to Gilead drug
Pregnancy (if applicable)	 Last menstrual period Date of pregnancy confirmation Estimated date of delivery or outcome if available at the time of the review

Prescription errors sub-study

After confirmation of eligibility criteria, investigators will collect the following data for each hospitalization episode selected, based on clinical/pharmacy/prescription records:

Individual characteristics (at the beginning of each hospitalization enigode)	- Subject initials (where permissible)
	- Date of birth
episode)	- Gender (male, female, transgender)
	- Race (White, Asian, Black or African heritage, other)
	- Non ART concomitant medications
Inpatient care (for each hospitalization	- Date of admission
episode)	- Admission diagnosis
	- Date of discharge
	- Discharge diagnosis
	- Destination at discharge
	- ICD-9 or ICD-10 code (primary and secondary)
	- DRG code Admitting service: HIV/AIDS, Medicine, Surgery, Obstetrics and Gynaecology, Neurology / Psychiatry, Other
	- Degree of the prescribing physician: Assistant / Junior doctor, Graduated Assistant / Registrar, Senior Graduated Assistant / Consultant, Other
	- Transferred within the first 48 hours? If so where to and when?
	- ART prescribed in the first 48 hours: active substances, dosage of each, scheduling
Prescription errors audit (for each error)	- Type of error:
Prescription errors audit (for each error)	 Type of error: (1) absence / incomplete regimen
Prescription errors audit (for each error)	 Type of error: (1) absence / incomplete regimen (2) incorrect dosage [including renal dose adjustment]
Prescription errors audit (for each error)	 Type of error: (1) absence / incomplete regimen (2) incorrect dosage [including renal dose adjustment] (3) incorrect schedule

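### The sub-study's unit of analysis contradicts its own eligibility rule and error list on omitted ART, and no rule says which regimen assigns an episode to STR or non-STR

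*Protocol*

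**What the plan says.** Three parts of the Protocol describe which hospital episodes belong to the prescription-errors sub-study.

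- **Unit of analysis (section 9.3):** an episode "in which there was a prescription of ART during the first 48 hours".
- **Inclusion criterion (section 9.2, repeated in the Synopsis):** patients "who received, or should have received, an ART regimen during the first 48 hours of the hospitalization episode". Step 2 of the selection procedure in section 9.3 applies this criterion: "the Investigator will check whether those hospitalization episodes meet the inclusion criteria".
- **Error type 1 (section 8.2):** this has two halves. One applies "when the regimen prescribed is incomplete"; the other applies "when the regimen is not prescribed although it should have been".

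On cohorts, the Synopsis and section 9.3 call for STR and non-STR groups. Section 9.3 also requires a separate list of episodes for each group, prepared before random sampling. The only ART regimen item in Table 3 (section 9.4) is "ART prescribed in the first 48 hours: active substances, dosage of each, scheduling". The other medication item there covers non-ART drugs.

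The endpoints concerned, in the Synopsis and section 9.1, are the share of episodes with an ART prescription error and the count of errors, each overall and by cohort.

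**The concern.** An admission in which ART was left off entirely passes the eligibility rule and is an error by definition, but does not fit the stated unit. Which sentence prevails determines whether such episodes are counted at all. Centers build their own lists, so they could resolve the conflict differently. The error proportion would then depend on local reading as well as on prescribing.

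The cohort question compounds this. An omission has no inpatient regimen to classify, and an erroneous order may not show what the patient was taking before admission. Unless the assigning regimen is named and recorded, the STR versus non-STR comparison rests on an unstated choice. Section 8 puts forward the hypothesis that STRs help avoid prescription errors, so the handling of omitted and incomplete regimens bears directly on it.

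**Working it through.** The sub-study has no sample-size or power figure to reproduce: section 9.6 says no formal determination was made and asks for about 40 episodes per center. The check is a comparison of texts, followed by arithmetic to show direction and possible size.

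**1. Three kinds of eligible episode**

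| Episode | Inclusion criterion (9.2) | Error type 1 (8.2) | Unit of analysis (9.3) |
|---|---|---|---|
| Complete ART regimen ordered | in | no | in |
| Incomplete ART regimen ordered | in | yes, incomplete half | in |
| No ART ordered although due | in | yes, absence half | **out** |

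The conflict lies in the third row only.

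**2. Effect on the error proportion if the unit is applied literally**

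Let *a* be the share of eligible episodes with no ART order although one was due (every one an error), and *b* the share with some other error. The two do not overlap, because the other errors need an order.

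- Following the inclusion criterion: *a* + *b*
- Following the section 9.3 unit: *b* / (1 − *a*)

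Both inputs are assumptions; the Protocol gives neither.

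- *a* = 0.10, *b* = 0.15: 0.25 against 0.15/0.90 = 0.167
- *a* = 0.05, *b* = 0.15: 0.20 against 0.15/0.95 = 0.158

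**3. The same effect from an error level cited in the Protocol**

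Section 7.2 cites a study with medication errors in 29% of admissions on the first day. Let *p* be the true error proportion and *s* the share of error episodes that are pure omissions (assumed). The section 9.3 unit then gives *p*(1 − *s*) / (1 − *ps*).

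- *p* = 0.29, *s* = 0.10: 0.261/0.971 = 0.27
- *p* = 0.29, *s* = 0.25: 0.2175/0.9275 = 0.23
- *p* = 0.29, *s* = 0.50: 0.145/0.855 = 0.17

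Per 40 eligible episodes, the number falling outside the unit is 40 × 0.29 × *s*, that is 1.2, 2.9 and 5.8. With *p* = 0.50, the error level section 7.2 cites from another study, the results are 0.47, 0.43 and 0.33.

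**4. Cohort assignment**

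The adherence study has a rule: section 9.3 groups subjects by the regimen they were receiving on 31 December 2013. The sub-study has none. From the fields in Table 3 as printed, an episode with no order cannot be placed in either cohort.

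To see what assignment by the inpatient order would do, assume 100 episodes in STR patients and 100 in non-STR patients, with 15 errors in each group and no true difference. Assume also that 5 of the STR patients' errors are incomplete orders that no longer contain the single tablet. Those 5 episodes would move to non-STR:

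- STR: (15 − 5)/(100 − 5) = 10/95 = 10.5%
- non-STR: (15 + 5)/(100 + 5) = 20/105 = 19.0%

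The contrast favours STR although the groups were built equal. This holds only if sites assign in that way.

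**The case against.** The strongest reply is that the section 9.3 sentence is loose wording and does not control the procedure. The operative steps search all admissions of HIV-1 infected patients and then apply the inclusion criteria, which admit omissions. The Synopsis endpoint carries no restriction to prescribed ART. A center following the steps would keep these episodes. This stands in part: exclusion is a consequence of the literal unit, not an established fact. It also confirms that two readings coexist.

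A reader might infer that the whole of error type 1 is lost. It is not; incomplete regimens involve an order and stay in.

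A reader might also infer that the cohort can be assigned only from the audited order, so that the outcome defines the exposure and the contrast is certainly biased. The Protocol does not support that. It is silent on the rule, and investigators work from clinical and pharmacy records as well as prescriptions. Judging that ART should have been given, or that a regimen is incomplete, already requires knowing the intended regimen. Nor is an STR patient correctly ordered the same drugs as separate tablets clearly an error under any of the six types, so such orders are left out of the illustration.

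Two further replies carry some weight. Section 9.10 admits that the sub-study is open to selection bias, but attributes this to the lack of matching, which is a different matter. A statistical analysis plan could name the cohort rule for the analysis. It could not recover episodes never listed or a pre-admission regimen never recorded, because the lists and the eCRF operate at data collection.

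**Conclusion.** The contradiction is in the text and needs no assumption: section 9.3 excludes from the unit an episode that section 9.2 admits and section 8.2 counts as an error. Applied literally, the unit understates the error proportion. Under the assumed rates the fall is from 25% to 16.7% or from 20% to 15.8%; starting from the cited 29%, it is to between 27% and 17% if 10% to 50% of error episodes are pure omissions. These figures show direction and plausible size; the Protocol gives no omission rate.

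The missing cohort rule is a second, separate gap. Any bias in favour of STR is conditional on assignment by the inpatient order. How the unit wording alone would affect the contrast is unknown, since it depends on omission rates by cohort.

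The primary endpoint is untouched. This concerns a secondary objective in a sub-study without a formal sample size, so it should be fixed, but it does not threaten the main study.

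**What to change.** 1. In section 9.3, change the unit of analysis to episodes in which ART was, or should have been, prescribed in the first 48 hours, so that it matches section 9.2 and the Synopsis.
2. In section 9.3, state that the STR and non-STR cohorts, and the two sampling lists, are defined by the ART regimen in use at admission.
3. Add that regimen as one field in Table 3 and the eCRF.

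The cost is two changes of wording and one data field, taken from records the investigator already reviews. No design figure changes, because the target of about 40 episodes per center is not derived from a formula.

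A separate minor item: the incorrect-dosage error in section 8.2 names renal dose adjustment but is then explained as "i.e. the dosage prescribed does not exist". An existing dosage not adjusted for renal function fits the first part and not the second. The two parts must be reconciled.

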	In this sub-study, two cohorts will also be considered: STR and non-STR however, unlike the adherence study, any ART regimen may be included. This is an analytical cross-sectional study aimed at identifying the proportion of hospital episodes in which prescription errors occur. A random sample of 40 hospitalization episodes will be selected according to the methods described below. Data will be collected by manual review of subject clinical records and types of errors classification will be performed by the investigator.	
Population:	Adherence study	
	HIV-1 infected adults who received ART between 1 st January 2009 and 31 st December 2013 for at least 90 days.	
	Inclusion criteria:	
	• HIV-1 infected	
	• Aged 18 or above at the beginning of the observation period	

 Able and willing to provide informed consent At least one pharmacy refill in 2013 Being followed at the center at the time of recruitment Has been on an ART regimen containing Stribild or one that is recommended by EACS v 7.0 {27774}(which contains two NRTI plus one NNRTI or two NRTI plus one PI/r) and which was taken once daily for at least 90 days on 31st December 2013 Availability of a complete electronic history of pharmacy refills throughout the observation period
 Subject participation in an interventional study during the observation period Subject on a non-pill formulation during the observation period Subject on off-ART periods (ART holidays) during the observation period
Patient-regimens permitted
For each subject to be included in the study, all regimens containing Stribild or all EACS v7.0 {27774} recommended ART regimens (which contain two NRTI plus one NNRTI or two NRTI plus one PI/r), and which were taken once daily for at least 90 days during the observation period, will be included in the analysis. EACS v7.0 alternative regimens will not be included, with the exception of regimens containing Stribild. These characteristics define a valid patient-regimen.
The regimen(s) may start before the beginning of the observation period or end after the observation period provided at least 90 days are within the observation period. In the case of a patient-regimen that continued after the end of the observation period, the patient-regimen will be censored at the date of the last refill within the observation period. The regimen duration to be considered is from the first refill of that regimen within the observation period to the last refill of that regimen during the observation period.

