	• Confounder adjusted actual (i.e. OIA adjusted) monthly ART plus hospitalization costs by patient-regimens adherence level (NA and OIA)	
	• Proportion of hospitalization episodes with ART prescription errors overall and in STR versus non-STR groups	
	• Percentage of prescription errors, overall and STR versus non- STR.	
	The list of confounders to be included is detailed in the variables to be collected section. All variables collected will be considered as confounders except the dependent or related dependent variable in question for each endpoint.	
Data Sources:	Centers participating in the Adherence study must have the complete history (within the observation period) of pharmacy refills available electronically in the hospital records. Subjects' clinical records will be the main source for the remaining data to be collected.	
	For centers participating in the Prescription errors sub-study, registration of ART errors, in either paper or electronic format, is required. The main source of data is thus the subject clinical record.	
Study Size:	Adherence study	
	700 STR subjects and 805 non-STR subjects is the sample size needed to enable a final sample size for analysis of 2060 patient-regimens (assuming an average of 1.5 patient-regimens per subject), after matching on a variable ratio with a propensity score approach. This is necessary to achieve a power of 80% for detecting a difference of 0.02 in the proportion of subjects with adherence > 90% between the two cohorts, with a two sided test with a significance level of 0.05, determined using the methodology proposed by Sahai and Khurshid {27760}.	
	Prescription errors sub-study	
	Due to the nature of the study design a formal size determination could not be performed. Each center will aim to include 40 inpatient care episodes of HIV-1 infected subjects that occurred between 1st	

	January 2012 and 29th December 2013. There is no minimum number of subjects required since the unit of observation is the hospitalization episode. The subjects enrolled onto the sub-study do not need to be participating in the adherence study in order to be eligible.	
Data Analysis:	Baseline characteristics will be reported using descriptive statistics. In general, when presenting descriptive statistics, the following parameters will be presented:	

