	• for qualitative data: absolute and relative frequencies. Proportions, and 95% confidence intervals for parameters of interest, will be based on the total number of subjects with non-missing values unless specified otherwise. Counts for missing values will be also tabulated but missing values will not be considered in the percentages	
	• for quantitative data: use of mean, standard deviation, median, 25th and 75th percentiles (interquartile range IQR), minimum and maximum and number of non-missing cases (95% confidence intervals for parameters of interest).	
	Adherence study:	
	Appropriate methods to deal with matched samples will be used. Suitable methods are Conditional Logistic Regression, Generalized Linear Mixed Models (GLMM) and Marginal Models (MM) with Gaussian or Logistic links.	
	Prescription errors sub-study:	
	The number of errors per hospitalization will be modeled with Generalized Linear Models (GLM). If significant correlation between hospitalizations from the same subject/hospital is found, then appropriate methods to address such data structure will be used. Suitable methods are GLMM and MM.	
	For both the main study and the sub-study:	
	Missing data will not be imputed.	
	In case of parametric procedures the underlying statistical assumptions, such as normality, will be checked. In case of severe violations of assumptions, transformations will be attempted as appropriate, and nonparametric methods may be used instead.	
	Exploratory post-hoc subgroup analyses may be performed if appropriate. All statistical tests will be two-tailed considering a significance level of 5%. Matching will be done using a propensity score approach on a variable ratio. The propensity score will be obtained using baseline and other retrospective information excluding	

any massing of adhering (outcome). The probability (propagaty) to
any measures of adherence (outcome). The probability (propensity) to
be in the STR group will be computed using logistic regression and
the cohorts matched using nearest neighbor (NN) matching algorithm
{27765} {27775}.

This study will be conducted in accordance with the guidelines of Good Pharmacoepidemiology Practices (GPPs) and Heads of Medicines Agencies (HMA) Good Pharmacovigilance Practices (GVP) including archiving of essential documents.

5. **AMENDMENTS AND UPDATES**

Amendment or Update Number	Date	Section of Study Protocol	Amendment or Update	Reason
<1>	[DD Month YYYY]	[Enter Text]	[Enter Text]	[Enter Text]

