- 3. Perform center level random sampling It is likely that the number of eligible episodes identified above is higher than the number of episodes the center is willing to include. In such case, each investigational center will select a sample of 40 episodes from their population, instead of including the entire population. Therefore, a sampling mechanism will be used. Episodes to be included will be randomly selected from the list of eligible episodes and stratification by cohort will be considered (stratified random sampling). In stratified random sampling, separate random samples will be selected from the two

cohorts created (STR and non-STR). Two separate lists with episodes' unique identifiers for each cohort will be prepared. The random samples will be obtained using Microsoft Excel®:

- The list of episodes' unique identifiers will be put in a column of an empty sheet;
- A second column will be created to the left (it must be to the left) of the patient-regimens' identifiers by writing "=RAND()" in each cell and random numbers from 0 to 1 will appear;
- The column with the random numbers will be copied and pasted as values in the same cells, so the random numbers won't change;
- Finally, the "Sort" button from the "Sort and Filter" group in the "Data" ribbon will be clicked (both "smallest to largest" or "largest to smallest" sorting may be used) and a randomly sorted list of episodes' identifiers will be obtained;
- Repeat the procedure for the other cohort.

The episodes to be selected are the first ones from each sorted list. As a guidance rule, even samples of episodes from each cohort should be obtained. Information of eligible hospitalization episodes shall be recorded on the eCRF.

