9.8. Data Analysis

The following general approach will be used:

for qualitative data - absolute and relative frequencies will be used. Percentages will be based on the total number of subjects with non-missing values unless specified otherwise. Counts for missing values will be also tabulated but missing values will not be considered in the percentages;

for quantitative data - mean, standard deviation, median, 25th and 75th percentiles, minimum and maximum, and number of non-missing cases (95% confidence intervals for parameters of interest) will be used.

Missing data will not be imputed.

In case of parametric procedures the underlying assumptions will be checked. In case of severe violations of assumptions, nonparametric methods will be used instead.

Exploratory post-hoc subgroup analyses may be performed if appropriate.

All statistical tests will be two-tailed considering a significance level of 5%.

The statistical analysis will account for the panel structure of the data.

Adherence study

Appropriate methods to deal with paired samples will be used. Suitable methods are Generalized Linear Mixed Models (GLMM), such as the Linear Mixed Model (for continuous outcomes, such as ART plus hospitalization costs), Poisson Mixed Model (for count outcomes, such as the number of days covered by treatment) or Logistic Mixed Model (for binary outcomes, such as the proportion of subjects with > 90% adherence). These models might be used as well when analyzing panel data. Other options might be to use Marginal Models (MM) which rely on Generalized Estimation Equations (GEE) for parameter estimation {27761} {27762}.

In order to reduce bias in treatment effect estimation, a propensity score will be obtained and covariate adjustment using the propensity score will be performed. In other words, the propensity score as well as the variable denoting the ART class will be entered in the appropriate regression model (for instance, binary logistic regression).

Prescription errors sub-study

The number of errors will be modeled with Generalized Linear Models (GLM). If significant correlation between hospitalizations from the same subject/hospital is found, then appropriate methods to address such data structure will be used. Suitable methods are GLMM and MM.

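### Prescription errors sub-study: an even STR/non-STR draw with no weighting back can bias the overall error proportion in either direction, and clustering is modeled only if it tests significant

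*Protocol*

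**What the plan says.** **Sampling.** Under Section 9.3 (Prescription errors sub-study), where more episodes are eligible than a center will include, "each investigational center will select a sample of 40 episodes from their population, instead of including the entire population". Two lists are prepared, one per cohort, and a separate random sample is drawn from each. On allocation: "As a guidance rule, even samples of episodes from each cohort should be obtained".

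**Target.** The Synopsis (Sub-study design) describes a cross-sectional study "aimed at identifying the proportion of hospital episodes in which prescription errors occur". Its secondary endpoints include: "Proportion of hospitalization episodes with ART prescription errors overall and in STR versus non-STR groups". Section 8.2 also asks for errors to be quantified overall and by cohort.

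**Denominator.** The only rule for forming proportions is the general one in the Synopsis (Data Analysis): "Proportions, and 95% confidence intervals for parameters of interest, will be based on the total number of subjects with non-missing values unless specified otherwise". Sampling fractions, weights and standardization to the true cohort mix are not mentioned.

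**Clustering.** The Synopsis and Section 9.8 both model the number of errors with a GLM and add: "If significant correlation between hospitalizations from the same subject/hospital is found, then appropriate methods to address such data structure will be used". Higher up in Section 9.8, before the two study parts are treated separately, a general sentence says without condition that the analysis will take the panel structure into account.

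**The concern.** There are two separate problems.

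1. Even allocation by cohort is a reasonable design for comparing STR with non-STR. It does not reproduce the cohort mix among hospitalized patients, and a flat 40 per center does not reproduce center caseload. An overall proportion pooled over such a sample estimates an artificial 50:50 mixture. It equals the population figure only if STR makes up about half of eligible episodes or if the two error rates are the same. The protocol's third research hypothesis (Section 8) is that STRs help to avoid prescription errors, so it expects the rates to differ.

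2. Episodes are sampled within hospitals, and one subject can contribute more than one episode because the unit is the episode. Correlation is therefore a feature of the design and not something to establish by a test. With few centers such a test has little power at small intraclass correlations (ICCs), and a non-significant result leads to intervals that are too narrow.

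At stake are the size of a stated secondary endpoint and the honesty of its interval.

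**Working it through.** The sub-study states no sample size, power or precision, so there is no figure to reproduce. What follows is illustration under stated assumptions.

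**Inputs**
- Allocation 1:1 and 40 episodes per center: Section 9.3.
- Non-STR error rate 29%: assumed, borrowed from the first-day admissions figure cited in Section 7.2.
- STR error rate 0.5 or 0.75 times that: assumed.
- STR share of eligible episodes, *w* = 0.20 to 0.65: assumed, since the protocol gives none.
- Nine centers: assumed. The adherence study implies 700/80 = 8.75 and 805/90 = 8.9; fewer may join the sub-study.
- ICC 0.01 to 0.10: assumed.

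**1. Overall proportion**

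Pooled 1:1 estimate: 0.5·pS + 0.5·pN. Population value: w·pS + (1 − w)·pN. The difference is (0.5 − w)(pS − pN).

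With pN = 0.29 and pS = 0.145 the pooled value is 0.5 × 0.145 + 0.5 × 0.29 = 0.2175.

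| STR share | Population value | Bias of pooled estimate |
|---|---|---|
| 0.20 | 0.2 × 0.145 + 0.8 × 0.29 = 0.261 | -4.4 points |
| 0.35 | 0.239 | -2.2 points |
| 0.50 | 0.2175 | 0 |
| 0.65 | 0.196 | +2.2 points |

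If the STR rate is 0.75 times the non-STR rate, the bias runs from -2.2 to +1.1 points. If the rates are equal it is 0. With the 72% literature maximum quoted in the protocol as the non-STR rate, and half of that for STR, it reaches 0.3 × (0.36 − 0.72) = -10.8 points at a 20% share.

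For scale, the naive 95% half-width with 360 episodes is 1.96 × √(0.29 × 0.71/360) = 4.7 points, so the largest bias in the table is about as big as the sampling error.

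**2. Clustering**

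Design effect = 1 + (40 − 1) × ICC: 1.39, 1.78, 2.95 and 4.90 at ICC 0.01, 0.02, 0.05 and 0.10. Multiplying 4.7 points by the square root of each gives half-widths of 5.5, 6.3, 8.1 and 10.4 points.

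Simulation: 9 centers × 40 episodes, beta-binomial, overall rate 29%, 20,000 runs. The center-heterogeneity chi-square is tested at 5%. The interval is naive if the test is not significant and a center-level t interval if it is.

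| ICC | Test significant | Coverage, clustering never modeled | Coverage, test first | Coverage, clustering always modeled |
|---|---|---|---|---|
| 0.01 | 19% | 91% | 92% | 95% |
| 0.02 | 37% | 86% | 91% | 95% |
| 0.03 | 53% | 82% | 90% | 95% |
| 0.05 | 75% | 75% | 92% | 95% |
| 0.10 | 94% | 63% | 93.5% | 94% |

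A re-run at an overall rate of 25% moved the detection, test-first and always-modeled columns by no more than about one point.

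**3. STR versus non-STR contrast**

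With 20 + 20 episodes in each of nine centers and center ignored, simulated type I error is 5.0%, 4.8% and 4.0% at ICC 0.02, 0.05 and 0.10. Balance within center largely protects this comparison from center clustering.

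**The case against.** - **The protocol never says the overall proportion is unweighted.** True. That is inferred from a general denominator rule, worded for subjects and open to exceptions, and from silence on weights. Weighting could be specified in an SAP that is not shown. However, weights need the eligible-episode counts by center and cohort. Table 3 lists data for selected episodes only and does not include those counts. Section 9.3 ends by sending information on eligible episodes to the eCRF, which may or may not cover the list lengths. If they are not recorded at the draw, the SAP has nothing to weight with unless centers are asked again.

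- **The even split is only guidance, and the sample of 40 applies only where more episodes are eligible.** Also true. A center that includes all its eligible episodes distorts its own cohort mix not at all.

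- **The general panel-structure sentence already covers clustering.** It conflicts with the specific conditional rule and does not displace it. The condition is also attached to the error-count model, so intervals for proportions have no clustering rule of their own beyond that general sentence.

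- **If inference is limited to the participating centers, hospital is a stratum.** Then the design effect and coverage figures above do not apply. Repeat episodes within a subject would still need handling, and the protocol does not state that restriction.

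- **This is a secondary endpoint with no formal sample size, and Section 9.10 concedes selection bias.** That limits the weight of the point. The concession, though, concerns the lack of matching and not this sampling feature.

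**Conclusion.** The point stands in limited form. The overall proportion *can* be biased, in either direction. Under the assumed rates of 29% and 14.5% the bias is -4.4 points at a 20% STR share, zero at 50% and +2.2 at 65%. Cohort-specific proportions are not biased by the even split. The test-first rule gives about 90-93% coverage for an overall rate over ICC 0.01-0.10, against 94-95% when clustering is always modeled, assuming nine centers of 40 episodes.

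A reader might infer more than the documents support:
- *That estimate and interval are both simply wrong.* There is no bias if the STR share is near 50% or the rates are equal.
- *That the overall figure is always pulled towards the STR rate.* That holds only if STR is the minority of episodes; the protocol gives no share.
- *That coverage falls to 86% or 72%.* At a 25% error rate those figures (ICC 0.02 and 0.05) hold only among runs where the test was not significant; they do not describe the whole procedure.
- *That the STR versus non-STR comparison is invalidated.* It is largely protected by balance within center.

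STR share, error rates, ICC and number of sub-study centers are all assumptions.

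**What to change.** 1. In Section 9.3, have each center record the lengths of its two eligible-episode lists, and make clear that the closing eCRF sentence covers these counts.
2. State that the overall proportion is weighted by the inverse sampling fraction for each center and cohort. Alternatively, drop the overall figure and report cohort-specific proportions only.
3. In the Synopsis and Section 9.8, delete the condition that correlation must first be significant. Always account for hospital and subject, both in the error-count model and in the confidence intervals of proportions. This also removes the conflict with the general panel-structure sentence.

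**Cost:** two counts per center, taken from lists that already exist for the random draw; a few lines of wording; and somewhat wider intervals for the overall figures.
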